9 PROCEDURES INVOLVED

This is a prospective randomized controlled trial comparing the early postoperative course of patients who undergo inpatient oncological procedures after assessment of their baseline physical activity before the surgery, using validated questionnaires in the clinic, to have a homogenized sample for the study. Participants will be randomized to the control arm (40 participants) and intervention group (40 participants). Control group participants will be asked to walk one to two laps around the ward twice per day, on the first day after the surgery following the usual clinical practice at Roswell Park Comprehensive Cancer Center-urology department (RPCCC). Their movement will be tracked with 3D motion tracking system (Xsens). The intervention arm participants will be asked to walk for minimum 30 minutes per day and their movement also will be tracked with Xsens. In both arms the patients will be asked to mobilize (walk out of the bed) on first day post-surgery under supervision and assistant of attending nurse in the floor if their clinical situation allowed. If patient cannot complete the walking tasks, they will be excluded from the study and they will be replaced by recruiting other patients.

Xsens is a wireless technology that makes use of sensors. The sensors are applied in a non-invasive manner and do not require the suit to be applied. There are various configurations of the sensors that can be utilized. The minimum number of sensors needed is 7. They are applied by using Velcro bands. The entire set-up takes about 5-10 minutes.

The study duration is 24 months or until target accrual is reached. In both arms their mobility will be tracked till they discharged from the hospital. In both arms we will assess the symptoms and signs of gastro-intestinal complications (nausea, vomiting, abdominal pain, passing flatus or stool) and chest symptoms (coughing, sputum, utilizing incentive spirometry) until they are discharged from the hospital. We will continue to follow them for 30 days post discharge to note any complications or readmission.

Patients at standard follow ups, 2 weeks, 6 weeks, 3 months or over the phone will complete a short post study questionnaire (Appendix B). The last three questions are taken from Woodfield et al., who assessed postoperative problems from the perspective of the patient on the identification of complications after surgery (11).

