4 LOCAL AND STUDY-WIDE NUMBER OF SUBJECTS

80 patients will be included in this study. All data will be identified and the duration of the study will be 24 months. Participant recruitment will occur through written informed consent prior the start of the study after thorough description.

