7 STUDY TIMELINES

The study duration is 24 months or until target accrual is reached. Subjects will be on study until they are discharged from the hospital. Subjects will be followed 30 days post discharge to note any complications or readmission. A post study questionnaire will be given to participants during one of their follow up visits which happen 2 weeks, 6 weeks, 3 months post discharge or over the phone if missed.

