10 WITHDRAWAL OF SUBJECTS

N/A

PROTOCOL TITLE: Does increased mobility assessed with 3D motion tracking technology lead to early post-operative recovery among patients undergoing oncologic surgeries

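### Randomised patients who cannot complete the walking tasks are excluded and replaced, so the analysis compares completers and not the randomised groups

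*Combined protocol and SAP*

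**What the plan says.** Section 9 sets the allocation: "Participants will be randomized to the control arm (40 participants) and intervention group (40 participants", and section 4 gives the total: "80 patients will be included in this study". Section 9 then gives each arm its own task. For control: "Control group participants will be asked to walk one to two laps around the ward twice per day", on the day after surgery. For intervention: "The intervention arm participants will be asked to walk for minimum 30 minutes per day". A third sentence applies to everyone: "In both arms the patients will be asked to mobilize (walk out of the bed) on first day post-surgery", with nursing supervision and only where the patient's condition permits. The rule in question comes directly after it: "If patient cannot complete the walking tasks, they will be excluded from the study and they will be replaced by recruiting other patients".

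Four other places could have protected the randomised comparison, and none does:

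- Section 7 provides follow-up ("Subjects will be followed 30 days post discharge to note any complications or readmission"), but for subjects of the study, and these patients have been removed from it.
- Section 10 reads, in full, "WITHDRAWAL OF SUBJECTS N/A".
- Section 16 specifies a mixed model for mobility, Fisher or chi-square tests for complications, and optional logistic regression. It names no analysis population and no missing-data rule.
- The sample-size paragraph of section 16 makes no allowance for attrition.

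**The concern.** Randomisation makes the arms comparable at the moment of assignment. Removing patients for something that happens afterwards, and that is plausibly linked to how they are recovering, breaks that. Inability to walk soon after surgery overlaps with what section 8 counts as recovery: nausea and vomiting, chest symptoms, discharge, complications and readmission.

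The rule leaves four things open:

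- **Which tasks are meant.** They could be the arm-specific tasks or the day-1 mobilisation common to both arms. Only on the first reading does the exclusion criterion differ by arm.
- **What counts as completion, and by which day it is judged.**
- **Where a replacement goes.** It could take the excluded patient's arm or the next slot on the block-of-4 list.
- **How many patients are randomised.** Any exclusion means more than 80.

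The direction of bias is conditional. If the tasks are arm-specific, more intervention patients fail, and failure goes with poor recovery, then the recovery endpoints and the complication test favour the intervention. For change in mobility the direction is unknown: bias arises only if completion is related to change, and that relation could have either sign. Even with equal exclusion the sample tends to lose its least mobile patients, and the second objective in section 1, a minimum useful level of mobility, needs them.

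**Working it through.** **The plan's own figure.** Section 16 gives 80% power for 0.63 SD with 40 per group, two-sided alpha 0.05, two-sample t-test. The noncentral t distribution gives 79.5% (normal approximation 80.4%), and the difference detectable at 80% is 0.634 SD. The stated figure reproduces.

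**Bias from excluding non-completers.** Exclusion fractions and correlations here are assumptions. Suppose a standard normal fitness score decides completion, the lowest fraction e is excluded, and the score has correlation r with a good outcome. The mean score among completers is λ(e) = φ(Φ⁻¹(1−e))/(1−e):

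- λ(0.05) = 0.109
- λ(0.10) = 0.195
- λ(0.20) = 0.350

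With no true effect, the spurious difference in SD units is r × [λ(e_int) − λ(e_ctl)]. Rejection rates come from simulated two-sided t-tests with 40 analysed per arm (100,000 trials per scenario).

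| Excluded, control vs intervention | r | Bias (SD) | Rejection |
|---|---|---|---|
| equal, or r = 0 | any | 0 | 5% |
| 5% vs 10% | 0.3 / 0.5 / 0.7 | 0.026 / 0.043 / 0.061 | 5.2 / 5.4 / 6.0% |
| 5% vs 20% | 0.3 / 0.5 / 0.7 | 0.072 / 0.121 / 0.169 | 6.2 / 8.5 / 13.0% |

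Example: 0.5 × (0.350 − 0.109) = 0.121. A negative r, which is possible for change in mobility, gives the same sizes against the intervention.

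**The same mechanism for complications.** Assume a true rate of 30% in both arms and 60% among non-completers. The rate among completers is (0.30 − e × 0.60)/(1 − e):

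- Control, e = 0.05: 0.27/0.95 = 28.4%
- Intervention, e = 0.20: 0.18/0.80 = 22.5%

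The gap of 5.9 percentage points is produced by the exclusions alone.

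**How many are randomised.** Assume 5% excluded in control and 10%, 20% or 30% in intervention.

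- Same-arm replacement to 40 per arm: 40/0.95 + 40/(1 − e) = 42.1 + 44.4, 50.0 or 57.1, so about 87, 92 or 99 patients.
- Next-slot replacement to 80 completers: about 41 vs 39, 43 vs 37 or 46 vs 34 analysed.
- Equal exclusion of 5% to 20%: 80/0.95 to 80/0.80, so about 84 to 100 patients.

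**The case against.** **Timing.** The protocol does not say when randomisation takes place. Section 3 requires an ambulant inpatient with a stay of at least two days, which can be confirmed only after surgery. If the tasks are the common day-1 mobilisation, the rule might be a late eligibility check applied alike to everyone. This does not succeed: section 9 describes even the common mobilisation as something asked of patients already in both arms, so on either reading the exclusion follows assignment. What stands is that equal exclusion of similar patients gives no bias under the null.

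**Size.** The harm depends on rates that nobody has stated, and the milder scenarios are negligible. That is correct. The case for change rests on losing the randomised comparison, not on any row of the table. The SD figures also suit a continuous outcome, whereas the directional argument concerns endpoints that are mostly present or absent. The complication example shows the same mechanism there, again on assumed rates.

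**Remedy.** Three points stand as refinements:

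- Extra recruitment is harmless if the original patients stay in follow-up and analysis.
- A mixed model on available sensor records assumes data missing at random, which is doubtful when inability to walk causes the gap.
- The power cost computed with no benefit in non-completers is a worst case.

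The conflict over withdrawal is a smaller, separate matter that can be corrected in the same edit.

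**Conclusion.** The concern holds and should be fixed before the rule is applied to patients, because outcomes not collected after exclusion may not be recoverable. That the analysed groups are completers follows from the text alone and needs no assumed rate. The size of the consequence does need one. With no true effect it runs from zero (equal exclusion, or completion unrelated to outcome), through 0.03 to 0.06 SD at 5% vs 10%, to 0.07 to 0.17 SD at 5% vs 20% with correlations of 0.3 to 0.7. It favours the intervention on recovery and complications only under the conditions set out above. For change in mobility the sign is unknown.

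**What to change.** **Section 9.** Delete the exclude-and-replace sentence. State that every randomised patient, unless consent is withdrawn, is followed to 30 days after discharge and analysed in the assigned arm whatever walking was done, with no replacement. If extra patients are wanted, plan them from the start, in addition to those already randomised. Define completion and when it is judged, and report completion and reasons for non-completion by arm. Whether a patient stops walking remains a clinical decision and is not touched.

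**Section 10.** Replace the not-applicable entry, which conflicts with sections 21 and 26, where participants may stop at any stage. Describe withdrawal of consent, and say that stopping the walking task is not withdrawal from follow-up.

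**Section 16.** Name the as-assigned population as primary and completers as a labelled sensitivity analysis. Use all available sensor records in the mixed model, report missing data by arm, and preferably add a sensitivity analysis that relaxes missing at random. Describe the 0.63 SD as the as-assigned effect.

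**Cost.** A few sentences, recording of completion, and follow-up of patients who would have been dropped. Recovery and complication outcomes do not need the sensors. There are two alternative statistical costs, both on assumed rates:

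- *Sensor data missing for non-completers* (80 randomised; 5% of control and 10%, 20% or 30% of intervention): 38 vs 36, 32 or 28 remain, and the detectable difference rises from 0.63 to 0.66, 0.68 or 0.71 SD.
- *0.63 SD is the completers' effect and non-completers gain nothing* (worst case): the as-assigned effect is 0.63 × (1 − e) = 0.567, 0.504 or 0.441 SD for 10%, 20% or 30% non-completion in the intervention arm. Power at 40 per arm is 0.71, 0.60 or 0.50, and 80% would need about 50, 63 or 82 per arm. If non-completers gain half the effect, power is about 0.75, 0.71 or 0.66.

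Part of the second cost is recoverable. Same-arm replacement would already mean randomising about 87, 92 or 99 patients in these scenarios. Planning that total from the start, split equally, gives worst-case as-assigned power of about 0.74, 0.67 or 0.59.

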10 WITHDRAWAL OF SUBJECTS

N/A

PROTOCOL TITLE: Does increased mobility assessed with 3D motion tracking technology lead to early post-operative recovery among patients undergoing oncologic surgeries

11 RISKS TO SUBJECTS

Risk of fall is associated with mobility. This will be minimized with standard procedures including; patient risk of fall stratification, supervised patient mobility and using balance assessment programs.

12 POTENTIAL BENEFITS TO SUBJECTS

There is no direct benefit to subjects.

13 DATA AND SPECIMEN BANKING

N/A

14 SAFETY REPORTING

N/A

15 DATA MANAGEMENT AND CONFIDENTIALITY

Data will be collected through computer logging, note taking, paper/pencil or computer forms. Demographic information (position title, years of experience, area of expertise) will be collected but names will not be associated with the data. Individual privacy will be maintained in all published and written data resulting from the study. Participants will be given a unique code/ID number. This number will be used instead of names to identify information collected during the study. De-identified data will be kept indefinitely, in paper and electronic form and on computers accessible to the investigators and their research assistants.

16 STATISTICAL PLAN

Demographics: Subject demographic and clinical characteristics will be reported by group using the appropriate descriptive statistics and graphical summaries. Comparisons will be made between groups using the Mann-Whitney U or Chi-square tests, as appropriate.

Randomization: Subjects will be randomized to the control and intervention groups in a 1:1 fashion using a permutation block design (block sizes = 4). The randomization list will be developed by the study statistician.

Primary Analysis: The primary objective is to evaluate changes in mobility between the control (standard of care) and intervention (additional activity) groups. The primary outcomes are measures of mobility (i.e. range of movement), which are treated as continuous measures and will be summarized by group and time-point using the mean, median, and standard deviation. The measures of mobility will each be modeled as a function of treatment group, time post-surgery, their two-way interaction, and random subject effects using a linear mixed model. Within each group, the effect of time on the mean will be evaluated using tests about the appropriate contrasts of model estimates. The effect of the two groups on the time-mobility relationship will be evaluated using an F-test about the interaction term. All model assumptions will be evaluated graphically and transformations will be applied as necessary.

Secondary Analyses: The secondary objective is to evaluate the impact on post-surgical complications. The complication status (present/absent) and grades will be summarized by group and compared using Fisher's exact test or the chi-square test, as appropriate.

PROTOCOL TITLE: Does increased mobility assessed with 3D motion tracking technology lead to early post-operative recovery among patients undergoing oncologic surgeries

The association between complication status and changes in measures of mobility may be evaluated using logistic regression models.

Sample Size Determination: The power calculations are based on the primary analysis, which compares the changes in measures of mobility between the two groups. Since the form of the models is unknown beforehand, a simplified and conservative power calculation is based on comparing the mean change (baseline to discharge) in a given mobility measure between groups using a two-sided, two-sample t-test. With a sample size of n=40 per group, we have 80% power (at $\alpha = 0.05$) to detect a difference of at least 0.63 standard deviations. Such a moderate effect size would be considered clinically relevant.

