5 LOCAL AND STUDY-WIDE RECRUITMENT METHODS

Subjects will be identified from the Roswell Park Comprehensive Cancer Center Genitourinary (GU) clinic and in the inpatient wards when they are scheduled for inpatient oncological surgical procedures. All clinic staff will be informed about the study to help with recognizing patients. When a potential patient is identified in clinic, one of the study team members will be notified and will discuss the study aims, risks and benefits. The subject will then be asked to sign an informed consent after proper review.

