20 SETTING

The potential subjects will be identified in the genitourinary clinic at Roswell Park Comprehensive Cancer Center where they will meet with one of the research team members and in the inpatient wards. The research procedure will be performed at Roswell Park Comprehensive Cancer Center inpatient wards.

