22 RESOURCES AVAILABLE

Our research team comprises of surgeons, clinical and research fellows, research assistants and coordinators. Our diverse team has worked on similar projects and has extensive experience in undergoing clinical trials. [name] laboratory, the Advanced Technologies Laboratory for Advanced Surgery (ATLAS) is located at Grace Cancer Drug Center is approximately 1400 sq. feet. A major portion of the lab is dedicated for industrial and human factor engineering researches and sciences. The laboratory is fully equipped to safely carry out and develop the proposed work. The laboratory personnel comprised of surgeons, clinical and research fellows, medical illustrators and engineers are highly experienced in conducting clinical research. The innovative multidisciplinary team utilizes the lab space for equipment storage and

PROTOCOL TITLE: Does increased mobility assessed with 3D motion tracking technology lead to early post-operative recovery among patients undergoing oncologic surgeries

data analysis. Space and network access are readily available throughout the study period. The PI, [name], and the research team members have their dedicated equipped work space with secretarial support. All participating research members will receive an in-service that adequately explains the research protocol, procedures and individual duties.

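### One fixed block size of 4, printed in the protocol of a single-centre trial with visible arms, could let a recruiter who follows the sequence foresee up to one third of allocations

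*Combined protocol and SAP*

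**What the plan says.** Section 16 (Statistical Plan, Randomization) states that "Subjects will be randomized to the control and intervention groups in a 1:1 fashion" "using a permutation block design (block sizes = 4"). It adds that "The randomization list will be developed by the study statistician". No other block size and no stratification factor is named.

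The surrounding facts come from other sections:

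- **Size.** Section 4: "80 patients will be included in this study". Section 9 splits them 40 and 40.
- **One centre.** Section 6 marks multi-site research as not applicable. Section 20: "The research procedure will be performed at Roswell Park Comprehensive Cancer Center inpatient wards".
- **Visible arms.** In Section 9 the control arm walks one or two ward laps twice a day and the intervention arm walks at least 30 minutes a day. Both are supervised by the floor nurse.
- **Who recruits.** Section 5: when a candidate is identified in clinic, "one of the study team members will be notified and will discuss the study aims, risks and benefits".
- **What the team knows.** Section 22: "All participating research members will receive an in-service that adequately explains the research protocol, procedures and individual duties".

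The documents do not say who holds the list, how an assignment is released, when randomisation happens relative to consent or surgery, or whether anyone is masked.

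**The concern.** In a 1:1 block of 4, two patients go to each arm. Once one arm's two places are used, the rest of the block is determined. Anyone who knows the block size and has followed the sequence can then name the next arm before deciding whom to approach, or when.

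Several features that make this feasible occur together here. The size is small, fixed and printed. There is apparently one list at one centre. The arms can be told apart by watching patients walk. Members of the same briefed team approach patients. Some eligibility criteria in Section 3, such as movement restricted by other disease, call for judgement.

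At stake is the comparability of the arms. If fitter or frailer patients were enrolled according to the expected arm, randomisation would no longer protect the comparison of mobility or recovery. The mixed model in Section 16 contains group, time, their interaction and subject effects, but no prognostic covariates that might absorb part of such an imbalance.

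**Working it through.** **Inputs.** Block size 4 and 1:1 allocation (Section 16); 80 patients (Section 4), 40 per arm (Section 9); no strata named, so one list. The plan gives no predictability figure to reproduce. Its layout is consistent: 80 / 4 = 20 blocks, and 20 × 2 = 40 per arm. The power statement in Section 16 (40 per group, 0.63 SD, 80%) also reproduces, at 79.5% by the exact t calculation, and is not affected by this point.

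**Step 1: certain allocations when every earlier one is known.** A block has 4! / (2! 2!) = 6 equally likely orders.

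- Positions 1 and 2 are never certain.
- Position 3 is certain when the first two match: 2/6 = 1/3.
- Position 4 is always certain.

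Expected certain allocations per block: 1/3 + 1 = 4/3. As a share: (4/3) / 4 = 33.3%. Over 20 blocks: 20 × 4/3 = 26.7, about 27 of 80. Each block has 2 certain allocations with probability 1/3 and otherwise 1, so the count is 20 + Binomial(20, 1/3), with a 95% range of 23 to 31.

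**Step 2: best guess, every earlier allocation known.** The observer names the arm with more places left.

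- Position 1: 1/2.
- Position 2: 2/3.
- Position 3: 1/3 × 1 + 2/3 × 1/2 = 2/3.
- Position 4: 1.

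Average: (1/2 + 2/3 + 2/3 + 1) / 4 = 70.8%, against 50% with no information.

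**Step 3: the latest allocations unseen.**

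- *One unseen.* Only position 4 can be certain, when the first two match: (1/3) / 4 = 8.3%, about 7 of 80. Best guess: (1/2 + 1/2 + 2/3 + 2/3) / 4 = 58.3%.
- *Two unseen.* At position 4 only the first allocation has been seen, so nothing is certain: 0%. Best guess: (1/2 + 1/2 + 1/2 + 2/3) / 4 = 54.2%.

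**Step 4: block sizes drawn at random from 4, 6 and 8.** Lists of 80 were simulated against an observer who knows the set of sizes and all earlier allocations but not the size of each block. The observer updates the probabilities after every patient, and ties count as one half.

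| Scheme | What the observer has seen | Certain | Of 80 | Best guess right |
|---|---|---|---|---|
| Fixed 4 | all earlier | 33.3% | 27 | 70.8% |
| Fixed 4 | all but the latest | 8.3% | 7 | 58.3% |
| Fixed 4 | all but the latest two | 0% | 0 | 54.2% |
| Random 4/6/8 | all earlier | about 2.3% | 2 | about 67.9% |

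Varying the size removes nearly all certainty but takes only about 3 percentage points off the best guess (70.8% to 67.9%). In the same simulation the two arms never differed by more than 4 patients at 80.

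**The case against.** The strongest reply is that one third is a ceiling. It needs a recruiter who knows the size and has seen every earlier allocation, in order, before the next enrolment decision. A reader might infer from the visible tasks that recruiters do see each assignment on the ward. The documents do not say so. Patients are identified in clinic or on the wards when scheduled for surgery, walking starts the day after surgery under the floor nurse, and the in-service is not said to cover allocation order. If patients are consented while earlier arms are still unseen, Step 3 applies and the figure may be near zero. This stands, and it sets the range. It does not close the point: the time of randomisation is not stated, and a team told each arm at randomisation would have no lag.

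There are partial safeguards. The statistician makes the list, consent must precede study procedures, and the ECOG and ASA limits narrow the room for choice. None of these stops someone from working out the end of a block.

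It is also fair to say that fixed blocks of 4 are a disclosed design choice and contradict nothing in the plan. The weakness comes from the combination with visible arms, one site and no stated release procedure. The reply is right, too, that varying the size does little against best guessing. The unstated concealment matters at least as much.

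**Conclusion.** The point holds as an avoidable opening for selection bias, with moderate confidence. The certain share lies between 0 and one third of allocations (0 to about 27 expected of 80), depending on how promptly recruiters learn earlier assignments. The upper end assumes a known block size, a single list and complete knowledge of the sequence.

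Two stronger readings are not supported. The first is that one third of allocations are certain as a matter of fact, or that steering takes place: nothing in the documents shows that recruiters track the sequence or act on it. The second is a stated bias in the treatment effect. That would need an assumed degree of steering, for which the documents give no figure. Moreover, a stable difference in prognosis between arms would not carry over one-for-one to the group-by-time test or to change from baseline to discharge. No size of bias is claimed.

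**What to change.** Three changes, to be made together:

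1. The study statistician generates the list with block sizes varied at random, for example 4, 6 and 8. If enrolment has begun, only the remaining part of the list is regenerated.
2. The block sizes come out of the protocol that staff receive and are kept in a file restricted to the statistician.
3. Section 16 states who holds the list, and that each assignment is released only after consent and eligibility have been recorded.

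The first change alone is not enough, because an observer who knows the set of sizes still guesses right about 68% of the time. The cost is a few lines in Section 16 and a regenerated list. It needs no extra patients. The downside is a possible final imbalance of a few patients instead of an exact 40 and 40.

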8 STUDY ENDPOINTS

The primary study endpoint is measuring early recovery of postoperative course by calculating early return of bowel motion (passing flatus and/or stool on which postoperative day), presence or absence of nausea and/or vomiting, presence or absence of chest symptoms (cough, sputum

PROTOCOL TITLE: Does increased mobility assessed with 3D motion tracking technology lead to early post-operative recovery among patients undergoing oncologic surgeries

and ability of using incentive spirometry), early discharge from the hospital and 30 days surgical related complications and readmissions.

The secondary study endpoint is measuring the range of joint movement in upper and lower joints of body, using the 3D motion tracking system (Xsens), to identify the minimum required level of mobility for better early postoperative course recovery.

A few other secondary endpoints concluded from the post experiment questionnaire include: assessing encouraged walking in the hospital setting subjectively improves their exercise habit outside of the hospital, how was the application of the sensors in a hospital setting as this is the first study to do so, and to assess the subjective impact of complications on quality of life.

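### Sections 8 and 16 name different primary endpoints (recovery versus range of movement); only mobility is powered, and day of bowel return and time to discharge have no named between-arm test

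*Combined protocol and SAP*

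**What the plan says.** Section 8 (Study Endpoints) states: "The primary study endpoint is measuring early recovery of postoperative course by calculating early return of bowel motion". It goes on to list nausea or vomiting, chest symptoms, and "early discharge from the hospital and 30 days surgical related complications and readmissions". On movement it states: "The secondary study endpoint is measuring the range of joint movement in upper and lower joints of body", and gives the purpose as finding the minimum mobility needed for better recovery.

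Section 16 (Statistical Plan), Primary Analysis, states: "The primary objective is to evaluate changes in mobility between the control (standard of care) and intervention (additional activity) groups", and then: "The primary outcomes are measures of mobility (i.e. range of movement), which are treated as continuous measures". Each mobility measure goes into a linear mixed model, with an F-test of the group-by-time interaction. Under Secondary Analyses: "The secondary objective is to evaluate the impact on post-surgical complications", and "The complication status (present/absent) and grades will be summarized by group and compared using" Fisher's exact or chi-square. A logistic model relating complications to mobility change is optional. Sample Size Determination refers only to mean change in a given mobility measure: 40 per group, two-sided two-sample t-test, alpha 0.05, 80% power at 0.63 SD.

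Section 1 (Objectives) lists the effect on recovery first but does not rank its objectives. The protocol title also asks about recovery.

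**The concern.** The two sections that should define the same primary endpoint define different ones, and both are current text. Under Section 8 the trial is decided by recovery. Under Section 16 it is decided by range of movement.

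The intervention arm is asked to walk more (Section 9), so a between-arm difference in a movement measure speaks mainly to what patients did. It does not answer the question in the title. While both definitions stand, either result could be presented as primary after the data are seen.

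Two of the components that Section 8 lists as primary, day of bowel return and time to discharge, have no stated between-arm comparison at all.

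**Working it through.** **1. The plan's own figure.** Inputs from Section 16: n = 40 per group, two-sided alpha 0.05, difference 0.63 SD.
- Normal approximation: power = Φ(0.63 × √(40/2) − 1.960) = Φ(2.817 − 1.960) = 80.4%.
- Exact noncentral t with 78 degrees of freedom: 79.5%. Power of 80% is reached at 0.634 SD.

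The figure is sound for the mobility measure it addresses.

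**2. Coverage of the Section 8 components by Section 16.**

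| Component | Status in Section 8 | Between-arm test in Section 16 |
|---|---|---|
| Day of flatus/stool | primary | none named |
| Nausea/vomiting | primary | Fisher or chi-square, only if counted as a complication |
| Chest symptoms | primary | same, only if counted as a complication |
| Discharge | primary | none named |
| 30-day complications | primary | Fisher or chi-square, as secondary |
| Readmission | primary | same, only if counted as a complication |
| Range of movement | secondary | mixed-model F-test, as primary |

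The sentence "Comparisons will be made between groups using the Mann-Whitney U or Chi-square tests, as appropriate" stands under Demographics and applies to demographic and clinical characteristics, so it does not fill the gaps. The optional logistic model relates complications to mobility, not to arm.

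Section 9 bears on the conditional rows in both directions. It describes nausea, vomiting and passing flatus or stool as signs of gastro-intestinal complications, which favours counting nausea and vomiting. It also names complications and readmission as separate items. A present/absent comparison would in any case not analyse the postoperative day of bowel return.

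**3. What 40 per arm could detect on recovery (illustration only).** The documents give no event rate, variance or target difference for any recovery component. The rates below are assumptions; tests are two-sided at 0.05.

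Complications, exact enumeration over two binomials with n = 40 each, for both tests that Section 16 allows (chi-square without continuity correction):

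| Assumed rates | Fisher | Chi-square |
|---|---|---|
| 30% vs 15% | 28% | 37% |
| 40% vs 20% | 41% | 50% |
| 30% vs 7% | 71% | 80% |
| 40% vs 13% | 73% | 80% |

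The smallest expected cell counts in the first two rows are 40 × 0.225 = 9 and 40 × 0.30 = 12, so chi-square would ordinarily be used there. Fisher reaches 80% at about 30% vs 5% (82%) or 40% vs 11% (82%).

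Time to bowel return, Schoenfeld formula with 1:1 allocation and 80% power: HR = exp(2 × (1.960 + 0.842)/√d). With d = 80 events this is exp(5.604/8.944) = 1.87. With 70 events it is 1.95, and with 60 it is 2.06. The formula ignores ties, and bowel return is recorded by whole day.

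Length of stay by rank test, if roughly normal: detectable shift = (1.960 + 0.842) × √(2/(40 × 3/π)) = 0.64 SD. The same normal approximation for the t-test gives 2.802 × √(2/40) = 0.63 SD, so the two are almost equal.

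**The case against.** Three points on the other side have force.

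First, a reader might infer a clean swap of primary and secondary. The documents do not support that. Section 8's secondary endpoint is movement measured to find a minimum threshold, whereas Section 16's primary is a between-arm change in movement. Of the recovery components, only complications are carried by name into Section 16's secondary objective. The sections conflict, but they are not mirror images.

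Second, a reader might infer that recovery goes untested. That is too strong. Complications have a named test, and Section 9's wording on gastro-intestinal signs may bring nausea and vomiting under it. The firm gap is day of bowel return and time to discharge. Chest symptoms and readmission depend on a definition that Section 16 does not give.

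Third, a reader might infer that the trial is underpowered for recovery. The documents support only the statement that no power calculation was made for it. Length of stay could do about as well as mobility. The low figures concern binary outcomes, rest on assumed rates, and are less severe by chi-square than by Fisher.

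None of this resolves the contradiction. Section 1 and the title lean towards recovery without ranking it, and no clause gives one section precedence.

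**Conclusion.** The concern holds. Sections 8 and 16 name incompatible primary endpoints, and the primary analysis as written does not test the endpoint that Section 8 calls primary. Day of bowel return and time to discharge have no named between-arm test. This must be settled, because it determines which result decides the trial and what a positive result would mean.

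The conclusion rests on the text alone and needs no assumption. The 80% power statement is arithmetically right but applies to mobility only. The recovery power figures depend on assumed inputs and show only that the detectable effect changes with the endpoint chosen.

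**What to change.** Before outcome data are analysed, amend Sections 8 and 16 so that they name the same primary endpoint.

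**If recovery is primary:**
- Choose one measure already collected, for example day of first flatus or stool, or length of stay. Alternatively, define a composite, or co-primaries with error control.
- Name its between-arm test, with a rule for patients discharged before the event and for tied days.
- Restate the detectable effect at 40 per arm.
- List the other components as secondary with named tests, and state which symptoms count as complications and whether readmission does.
- Make the mobility mixed model secondary.

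**If mobility is primary:**
- Change Section 8 to match.
- Name one primary mobility measure, or add error control. Section 16 has several primary outcomes, each modelled separately, so aligning the labels alone would still not fix which result decides the trial.
- List the recovery components as secondary with named tests.
- Limit the primary conclusion to range of movement, and state that no power calculation was made for recovery.

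The title and the unranked objectives in Section 1 can stay in either case.

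The cost is a protocol and SAP amendment. Sections 8 and 9 already provide for collecting the outcomes, so no new procedures are needed. No extra patients are needed if the sponsor accepts the detectable effect at 40 per arm. The downside is that this effect may be less favourable for a binary or time-to-event measure. Bowel return and stay may also vary between procedures, since any oncologic surgery is eligible.
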